7 DATA HANDLING AND RECORD KEEPING.....	15
7.1 CONFIDENTIALITY.....	15
7.2 SOURCE DOCUMENTS.....	15
7.3 RECORDS RETENTION	16
8 STUDY MONITORING, AUDITING, AND INSPECTING.....	16
8.1 STUDY MONITORING PLAN	16
8.2 AUDITING AND INSPECTING	17
9 ETHICAL CONSIDERATIONS.....	17
10 STUDY FINANCES	17
10.1 FUNDING SOURCE	17
11 PUBLICATION PLAN	17

12	REFERENCES	18
13	ATTACHMENTS	ERROR! BOOKMARK NOT DEFINED.

LIST OF ABBREVIATIONS

EUS	Endoscopic Ultrasound
MRE	Magnetic Resonance Elastography
AE	Adverse Event/Adverse Experience
CFR	Code of Federal Regulations
CRF	Case Report Form
DSMB	Data and Safety Monitoring Board
FDA	Food and Drug Administration
GCP	Good Clinical Practice
HIPAA	Health Insurance Portability and Accountability Act
IRB	Institutional Review Board
PHI	Protected Health Information
PI	Principal Investigator
SAE	Serious Adverse Event/Serious Adverse Experience
SOE	Schedule of Events
SOP	Standard Operating Procedure
E	Elastic Modulus
V _s	Shear wave velocity
V _{sN}	Reliability Index
IQR/M	Interquartile Range/Median

Study Summary

Title	A Prospective Study of Endoscopic Ultrasound Shear Wave Elastography for assessment of liver fibrosis
Running Title	EUS shear wave elastography VS MRE
Title Acronym	EUS vs MRE
IRB Protocol Number	21-003779
Phase	Prospective comparative study
Methodology	Subjects who are eligible will undergo EUS for clinical indications. After completion of EUS, subjects will undergo subsequent MR Elastography if not already performed for clinical purposes. EUS Shear wave measurements will be studied to determine diagnostic accuracy when compared to MR Elastography.
Overall Study Duration	6 months Recruitment and Active study execution, 3 months analysis and 3 months publication. Total: 12 months
Subject Participation Duration	Up to 60 days screening prior to study procedure, and up to 60 days post procedure to follow-up MRE.
Objectives	To assess the diagnostic accuracy of EUS shear wave elastography in liver fibrosis staging in both normal subjects and subjects with advanced liver fibrosis/cirrhosis
Number of Subjects	Fifty (50)
Diagnosis and Main Inclusion Criteria	Subjects over 18 years of age who are scheduled to undergo endoscopic ultrasound procedure as part of clinical care.
Study Device	EUS shear wave elastography
Reference Imaging Modality	Magnetic resonance elastography (MRE)
Statistical Methodology	All continuous variables will be expressed as mean and standard deviation. Categorical variables will be expressed as percentages. Multivariate analysis will be performed.

1 Introduction

This document is a clinical research protocol relating to the prospective study on endoscopic ultrasound (EUS) shear wave elastography in assessment of liver fibrosis. The described study will be conducted in compliance with this protocol, applicable United States government regulations and Mayo Clinic policies and procedures.

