1.4 Study Rationale and Risk Analysis (Risks to Benefits Ratio)

1.4.1 Study Rationale

Revised 6/1/2021

Patients with chronic liver disease who are suspected to have advanced fibrosis will often undergo endoscopy for a variety of reasons (e.g. variceal screening). If successful and reliable, EUS-SWE will enable us to provide single session, comprehensive assessment of the liver including fibrosis staging and screening for complications of advanced liver disease such as gastroesophageal screening and liver cancer. The perceived practical advantages include reduced number of appointments, thereby confers cost and time benefits for the patients. Furthermore, EUS obviates the need for shear waves to travel through abdominal wall and visceral adiposity, hence provides unobstructed views of the liver in which accurate measurements can be obtained. This is particularly beneficial in many patients with non-alcoholic fatty liver disease (NAFLD) associated with significant underlying obesity (e.g. BMI > 35), where other imaging modalities often under-performs due to BMI limitations.

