1.4.3 Potential Benefits

If successful and reliable, EUS-SWE will enable us to provide single session, comprehensive assessment of the liver including fibrosis staging and screening for complications of advanced liver disease such as gastroesophageal screening and liver cancer. The perceived practical advantages include reduced number of appointments, thereby confers cost and time benefits for the patients.

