2.1 Primary Objective

To evaluate the diagnostic performance of EUS shear wave elastography in the assessment of liver fibrosis compared to MR elastography.

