3.1 General Design

This is a prospective, paired study. Study subjects who are scheduled to undergo EUS at Mayo Clinic will be identified through Epic. Chart review will be performed including review of prior imaging, medical history, and laboratory results as available in Epic to determine study eligibility. Subjects without history of chronic liver disease (screened by low FIB-4 score) and those with known advanced fibrosis/cirrhosis will be eligible for the study. Eligible study subjects will then be contacted either before, or at the time of their endoscopy procedure to discuss study participation. All subjects will then receive standard clinical care based on the indication for the EUS procedure. During the EUS procedure, study subjects with undergo shear wave measurements obtained in a non-invasive manner as part of the endosonographic evaluation of the liver. 10 measurements (including shear wave velocity (Vs), elastic modulus (E)) will be obtained for point SWE (pSWE). Measurements will be obtained from both left and right lobes of liver unless technically infeasible to do so. Study subjects will then undergo a paired MR elastography (same day or at later date) after completion of EUS and only if consistent and reliable shear wave measurements were obtained (e.g., VsN > 70% (reliability index of each measurement expressed in percentages), IQR/M (interquartile range/ Median) is <15% for Vs and <30% for E). Enrolled study subjects who had undergone a previous MRE (within 6 months of enrollment) would be eligible for the study, without the need to undergo further research MRE. After completion of MR elastography, the subjects will then continue through their routine clinical care and will not be followed up by research staff. The expected duration of subject participation is anticipated to begin at the time of study enrollment and terminate after completion of MR elastography. There will be no additional follow up.

3.2

Figure 1: Study Design

[figure not shown]

Table 1: Schedule of Events (SOE)

	Baseline Screening & Enrollment Visit 1 Days -180 to 0	Accrual: Study Intervention Visit 2 Day 0	Follow up Visit 3 Days 0 to 60
Inclusion/Exclusion	X		
EUS and Shear wave Elastography		X	
MRE	X*		X*

**MRE only required to be conducted once. Patients undergoing MRE for clinical purposes within the study timeframe can be recruited using the clinically performed MRE result.*

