3.4 Primary Safety Endpoints

There are no specific primary safety endpoints pertaining to the study as EUS shear wave and MR elastography are non-invasive investigations. There is no investigational device involved in this study.

4 Subject Selection, Enrollment and Withdrawal

All patients who are undergoing EUS procedures may be eligible for the study. Patients with an established history of chronic liver disease with associated advanced fibrosis/cirrhosis will be of particular interest to the study.

It is anticipated that we will screen up to 250 subjects and enroll 50 subjects to the study.

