4.1 Inclusion Criteria

1. Adults over 18 years of age who are undergoing EUS procedures.
2. Subjects with history of chronic liver disease, advanced fibrosis, or cirrhosis.
3. Subjects without any history of chronic liver disease.
4. Subjects able to give appropriate consent to the study.

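### The stated aim of fibrosis staging goes beyond a plan whose hypothesis contrasts two extremes, whose sections disagree on enrolling intermediate disease, and whose analysis sets no stage thresholds

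*Combined protocol and SAP*

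**What the plan says.** **The aim.** The Objectives row of the Study Summary reads "To assess the diagnostic accuracy of EUS shear wave elastography in liver fibrosis staging in both normal subjects and subjects with advanced liver fibrosis/cirrhosis". Section 2.1 is looser: "To evaluate the diagnostic performance of EUS shear wave elastography in the assessment of liver fibrosis compared to MR elastography". Section 3.3.3 is worded much like 2.1. Neither 2.1 nor 3.3.3 uses the word staging.

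**The use in view.** Section 1.4.1 opens with "Patients with chronic liver disease who are suspected to have advanced fibrosis will often undergo endoscopy for a variety of reasons". Sections 1.4.1 and 1.4.3 both hold out, if the method works, a "single session, comprehensive assessment of the liver including fibrosis staging".

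**Who is enrolled.** Section 3.1 states: "Subjects without history of chronic liver disease (screened by low FIB-4 score) and those with known advanced fibrosis/cirrhosis will be eligible for the study". The opening of section 4 states: "All patients who are undergoing EUS procedures may be eligible for the study", and describes advanced disease as being of particular interest. Inclusion criterion 2 in section 4.1 is "Subjects with history of chronic liver disease, advanced fibrosis, or cirrhosis", and criterion 3 admits people with no such history. Section 4.2 excludes no fibrosis stage.

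**What is tested.** Section 5.1 hypothesises non-inferiority to MRE in telling cirrhosis from no fibrosis. It cites AUCs of 0.972 for MRE and 0.89 for EUS-SWE from preliminary work. Section 12 describes the pilot as separating normal stiffness from advanced fibrosis or cirrhosis. Section 5.2 plans the AUC of EUS-SWE with MRE as the standard, and names no stage cut-off, per-stage AUC or ordinal analysis.

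**The concern.** Staging means placing a patient along the whole range from no fibrosis to cirrhosis. The hard part is the middle of that range. Comparing people thought to have healthy livers with people already known to have advanced disease leaves the middle out, so it answers an easier question.

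The rationale is about patients in whom advanced fibrosis is suspected but not settled. Both groups in section 3.1 have been sorted before the test is done, and suspected disease is in neither.

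Section 1.3 presents this as the first prospective comparison of EUS-SWE with MRE, and section 11 plans publication. If the objective stays worded as staging, a high AUC from the two-group contrast could be reported as evidence of staging accuracy, although the plan contains no analysis that measures it.

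**Working it through.** **Step 1. Set the sections side by side.**

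| Place | Who or what | Intermediate disease? |
|---|---|---|
| Summary objective | Staging, in normal and advanced/cirrhotic subjects | Implied by staging, absent from the groups named |
| 1.4.1, 1.4.3 | Staging where advanced fibrosis is suspected | Yes |
| 3.1 | No liver disease (low FIB-4), or known advanced fibrosis/cirrhosis | No |
| 4, 4.1 | Any EUS patient; chronic liver disease of any stage | Permitted, not ensured |
| 5.1 | Cirrhosis against no fibrosis | On neither side |
| 5.2 | One AUC against MRE | No threshold given |

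If 3.1 governs, there are no intermediate subjects on whom to test staging. If 4.1 governs, there may be some, but 5.1 does not say on which side they fall and 5.2 gives no cut-off to classify them. A staging conclusion is unsupported either way.

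**Step 2. Illustrate the direction and possible size.** The only EUS-SWE figure is the AUC of 0.89 in 5.1. It is taken as given, since no pilot data are shown from which to recompute it. The rest of this step is assumption: normal distributions with equal variance, five ordered grades from F0 (none) to F4 (cirrhosis), and 0.89 read as the AUC of F0 against F4.

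- Separation of the extremes: d = √2 × Φ⁻¹(0.89) = 1.414 × 1.2265 = 1.735.
- A grade at fraction s of the way from F0 to F4 is separated from F4 with AUC = Φ(1.2265 × (1 − s)).
- Halfway, s = 0.5: Φ(0.613) = 0.730.
- Neighbouring grades with equal spacing: Φ(1.2265 × 0.25) = Φ(0.307) = 0.62.

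The AUC for F4 against F0–F3 is the average of these terms, weighted by the shares of F0 to F3.

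| Positions of F0–F4 | Terms for F0, F1, F2, F3 | Equal shares | Mild-weighted | Mid-weighted |
|---|---|---|---|---|
| 0, 0.25, 0.50, 0.75, 1 | 0.890, 0.821, 0.730, 0.620 | 0.765 | 0.805 | 0.743 |
| 0, 0.10, 0.25, 0.55, 1 | 0.890, 0.865, 0.821, 0.710 | 0.821 | 0.848 | 0.810 |
| 0, 0.05, 0.15, 0.40, 1 | 0.890, 0.878, 0.851, 0.769 | 0.847 | 0.865 | 0.840 |

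The assumed F0–F4 shares are 20% each (equal), 35/25/20/10/10% (mild-weighted) and 10/25/30/25/10% (mid-weighted). The two ends of the range are:

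- Lowest: (10 × 0.890 + 25 × 0.821 + 30 × 0.730 + 25 × 0.620)/90 = 0.743.
- Highest: (35 × 0.890 + 25 × 0.878 + 20 × 0.851 + 10 × 0.769)/90 = 0.865.

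The range is therefore about 0.74 to 0.87. With the cut at F3 or above, the same model gives about 0.71 to 0.79.

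A simpler version has one intermediate class, halfway, forming a fraction f of the non-cirrhotic group: AUC = (1 − f) × 0.89 + f × 0.730. This gives 0.858, 0.837 and 0.810 for f = 0.20, 0.33 and 0.50.

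**Step 3. Precision of a correlation within the liver-disease group.** The group size is not stated; assume 25 of the 50. By Fisher's z (approximate for Spearman), an observed ρ of 0.5 gives z = 0.549 with standard error 1/√22 = 0.213. The limits are tanh(0.549 ± 1.96 × 0.213), or about 0.13 to 0.75.

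**The case against.** A reader of section 3.1 might infer that the study recruits only the two extremes and that its AUC is therefore inflated. The documents do not support so flat a statement. Section 4 and criterion 2 of section 4.1 admit chronic liver disease at any stage, so the eventual case mix is open and any inflation depends on 3.1 governing. For the question posed in 5.1, cirrhosis against no fibrosis, the AUC is not inflated at all.

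Three further points can be made for the plan:

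- Among the stated objectives, staging appears only in the Summary, in a sentence that itself names the two groups.
- The staging benefit in 1.4.1 and 1.4.3 is conditional, a hope for later use and not a conclusion this study promises.
- A wide contrast is a legitimate choice for a first comparison that follows a small pilot.

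All of this stands, and it narrows the point. It does not remove it. Permitting intermediate disease does not ensure that any is enrolled, and without thresholds in 5.2 such subjects could not be used to assess staging. An open case mix also means that a reader could not tell which population the AUC describes.

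The figures in the working are also fairly challenged: spacing and mix are assumed. The direction is the same in every combination tried, but no single value should be quoted as the expected loss.

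**Conclusion.** The concern holds in a limited form. The planned AUC is valid for the contrast in 5.1 and cannot support a conclusion about staging, whichever eligibility text applies. This rests on the wording alone and needs no modelling.

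That the AUC would be too high for suspected or intermediate disease is an expectation, conditional on recruitment following 3.1. Its size cannot be derived from the documents. The fall from 0.89 to about 0.74–0.87 is an illustration that rests on the equal-variance normal model, the three spacings, the three mixes, and reading 0.89 as no fibrosis against cirrhosis. The pilot's diseased group in section 12 also included advanced fibrosis.

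The conflict between 3.1 with 5.1 on one side and 4 with 4.1 on the other is a defect in its own right and must be settled first, because the right wording of the objective depends on it. The matter should be corrected, but it does not invalidate the study.

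**What to change.** 1. Reconcile sections 3.1 and 5.1 with sections 4 and 4.1, stating whether subjects with intermediate disease are enrolled.
2. If they are not, replace the staging wording in the Summary objective with discrimination between subjects without liver disease and subjects with known advanced fibrosis/cirrhosis. Bring the broader wording of 2.1 and 3.3.3 into line, and state that the AUC does not extend to suspected or intermediate disease. If they are, prespecify in 5.2 the MRE stage cut-offs and an AUC at each threshold, and report the case mix.
3. In either case, add to 5.2 a Spearman correlation of SWE with continuous MRE stiffness, overall and within the liver-disease group. Label it descriptive. It does not measure staging accuracy, the within-group estimate will be imprecise, and a restricted range of disease may attenuate it.

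The first route costs a narrower claim. The second costs some added specification, and since the case for 50 subjects in 5.1 was made for the two-group contrast, it would need revisiting. The correlation uses values already collected. Neither route requires recruitment to be widened or procedures to be added.

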1.1 Background

Shear wave elastography (SWE) uses shear waves to assess tissue elasticity in a non-invasive fashion. This technology has been incorporated into conventional trans-abdominal ultrasonography to evaluate for liver stiffness, especially in patients with suspected chronic liver disease. Endoscopic assessment of the liver is routinely performed during endoscopic ultrasound (EUS). Recent software package enhancements have allowed for the option of shear wave measurement during EUS procedures. To date, there is little to no literature on the performance of EUS SWE and its applicability in the assessment of liver fibrosis in the clinical setting. Therefore, we wish to determine the applicability of EUS SWE and evaluate its diagnostic accuracy compared to magnetic resonance imaging elastography, which is widely utilized to determine the presence of advanced fibrosis/cirrhosis in current clinical practice.

1.2 Investigational Device

EUS shear wave is available commercially, through a software package upgrade on the existing EUS machine. The Olympus Aloka Arietta 850 EUS processor and shear wave elastography software package are FDA-approved devices that have been purchased for clinical purposes and is being used in clinical practice. Shear wave measurements are obtained by the press of a button on the EUS machine to switch on the SWE software and measurements obtained.

1.3 Clinical Data to Date

Currently there is no available literature that systemically evaluates the performance of EUS shear wave elastography. Our study would provide the first prospective, comparative evaluation of EUS SWE with MR elastography, which is a widely adopted non-invasive imaging modality utilized for liver fibrosis assessment.

1.4 Study Rationale and Risk Analysis (Risks to Benefits Ratio)

1.4.1 Study Rationale

Revised 6/1/2021

Patients with chronic liver disease who are suspected to have advanced fibrosis will often undergo endoscopy for a variety of reasons (e.g. variceal screening). If successful and reliable, EUS-SWE will enable us to provide single session, comprehensive assessment of the liver including fibrosis staging and screening for complications of advanced liver disease such as gastroesophageal screening and liver cancer. The perceived practical advantages include reduced number of appointments, thereby confers cost and time benefits for the patients. Furthermore, EUS obviates the need for shear waves to travel through abdominal wall and visceral adiposity, hence provides unobstructed views of the liver in which accurate measurements can be obtained. This is particularly beneficial in many patients with non-alcoholic fatty liver disease (NAFLD) associated with significant underlying obesity (e.g. BMI > 35), where other imaging modalities often under-performs due to BMI limitations.

1.4.2 Anticipated Risks

There would be no additional anticipated risks associated with EUS shear wave elastography. Patients will undergo EUS procedure as clinically indicated and therefore would be subjected to the standard procedural risks associated with performing EUS.

1.4.3 Potential Benefits

If successful and reliable, EUS-SWE will enable us to provide single session, comprehensive assessment of the liver including fibrosis staging and screening for complications of advanced liver disease such as gastroesophageal screening and liver cancer. The perceived practical advantages include reduced number of appointments, thereby confers cost and time benefits for the patients.

1.5 Anticipated Duration of the Clinical Investigation

The overall duration of the study is estimated to be six to twelve months. There will be no planned follow up at the completion of the MRE.

2 Study Objectives

2.1 Primary Objective

To evaluate the diagnostic performance of EUS shear wave elastography in the assessment of liver fibrosis compared to MR elastography.

2.2 Secondary Objective

1. Explore the predictive value of EUS shear wave elastography in prognosticating patients with chronic liver disease and its complications.

3 Study Design

3.1 General Design

This is a prospective, paired study. Study subjects who are scheduled to undergo EUS at Mayo Clinic will be identified through Epic. Chart review will be performed including review of prior imaging, medical history, and laboratory results as available in Epic to determine study eligibility. Subjects without history of chronic liver disease (screened by low FIB-4 score) and those with known advanced fibrosis/cirrhosis will be eligible for the study. Eligible study subjects will then be contacted either before, or at the time of their endoscopy procedure to discuss study participation. All subjects will then receive standard clinical care based on the indication for the EUS procedure. During the EUS procedure, study subjects with undergo shear wave measurements obtained in a non-invasive manner as part of the endosonographic evaluation of the liver. 10 measurements (including shear wave velocity (Vs), elastic modulus (E)) will be obtained for point SWE (pSWE). Measurements will be obtained from both left and right lobes of liver unless technically infeasible to do so. Study subjects will then undergo a paired MR elastography (same day or at later date) after completion of EUS and only if consistent and reliable shear wave measurements were obtained (e.g., VsN > 70% (reliability index of each measurement expressed in percentages), IQR/M (interquartile range/ Median) is <15% for Vs and <30% for E). Enrolled study subjects who had undergone a previous MRE (within 6 months of enrollment) would be eligible for the study, without the need to undergo further research MRE. After completion of MR elastography, the subjects will then continue through their routine clinical care and will not be followed up by research staff. The expected duration of subject participation is anticipated to begin at the time of study enrollment and terminate after completion of MR elastography. There will be no additional follow up.

3.2

Figure 1: Study Design

[figure not shown]

Table 1: Schedule of Events (SOE)

	Baseline Screening & Enrollment Visit 1 Days -180 to 0	Accrual: Study Intervention Visit 2 Day 0	Follow up Visit 3 Days 0 to 60
Inclusion/Exclusion	X		
EUS and Shear wave Elastography		X	
MRE	X*		X*

**MRE only required to be conducted once. Patients undergoing MRE for clinical purposes within the study timeframe can be recruited using the clinically performed MRE result.*

